6.4 Randomization

Participants who complete all baseline assessments will be randomized in a 1:1 fashion to either BBTI plus eszopiclone or BBTI using a stratified permuted block randomization scheme. The proposed assignment method has been shown to effectively create similar groups of participants across treatment conditions ⁹. The randomization list will be generated by the study biostatistician. Subjects will be included in data analyses according to their randomized assignment irrespective of the treatment received (intent-to-treat).

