6.5 Intervention

Prior to initiating treatment, patients will be studied for the fitting of a nasal or oronasal facemask using a custom fitting chart. The appropriate sized facemask and head strap will be used that provides maximum patient comfort and minimizes leaks around the mask. All patients will be taught how to properly fit the mask and head strap and remove it and maintaining its care. Sleep hygiene education will be provided about the effects of caffeine, alcohol, and exercise on sleep, and the effects of noise, light, and excessive temperature. All participants will receive a standardized education session with their bed partner (if possible) designed to improve their CPAP adherence. They will also receive an educational brochure, which is reviewed by the respiratory therapist. In addition to motivational content to promote adherence, the brochure will cover what CPAP is, why regular use is important, care and daily cleaning of the mask, how to troubleshoot mask-related problems, how to perform weekly cleaning of the mask and the device, care, and cleaning of the humidifier, and general care of the device. The respiratory therapist will also demonstrate the described techniques using an unpowered unit. At each telephone call and follow up visit, participants will be prompted for any CPAP-related problem using the CPAP troubleshoot checklist. In case a problem is identified, the respiratory therapist will contact the participant to address the problem.

A. Brief Behavior Treatment of Insomnia-Military Version

Detailed descriptions of BBTI efficacy data and therapeutic guidelines have been previously reported ¹⁰⁻¹². BBTI is adapted from a manualized behavioral treatment as described previously ¹¹. BBTI will be delivered over four consecutive weeks, and includes one individual in-person visit (45 min) at week 1, a second in-person visit at week 3 (<30 min), and brief telephone appointments during weeks 2 and 4 (<20 min each).

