In addition to CBT-I, participants randomized to the combination therapy will receive eszopiclone 2 mg orally at bedtime or placebo starting with the CBT-I sessions for a period of 2 weeks. A brief in person (20-30 minutes) consultation session during the enrollment visit will be provided to review potential side effects that could arise from the medication. The Patient Monitoring Checklist will be obtained at baseline (enrollment), week 1, and at week 2. The study pharmacist will review the Patient Monitoring Checklist to assess for serious adverse events. Patients will be encouraged to comply with the medication regimen. Medication adherence will be determined by self-report and pill counts at end of treatment.

C. CPAP device

Participants will be instructed to adhere to CPAP utilization (at least 4 hours per night) on the first night after treatment is initiated. All participants will be provided with a REMstar Pro CPAP (Respironics Inc., Murrysville PA) device operated in automatic mode with a data-storage SmartCard at no cost. The data card records time while the mask is on the face. The returned data cards will be downloaded by staff who will be blinded to the treatment arms and automatically analyzed using the Encore Pro software (Respironics Inc., Murrysville PA).

6.6 *Follow-up Study visits*

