Follow up visits for all participants will be scheduled at EOT and at 6-month. At each of the scheduled follow-up visit, participants will be asked to complete the PSQI, ESS, PCL-5, ISI, and BDI-II. The list of medications will be reviewed and any changes in prescribed and non-prescribed medicines will be recorded. Potential adverse events will be assessed including hospitalization, and extreme sleepiness (such as while driving, operating machinery, cooking, or in other unsafe situations). A random urine toxicology testing will be conducted. During these follow-up visits, adherence to CPAP will be assessed by downloading the SmartCard data by a respiratory therapist blinded to the treatment intervention. At the end of 6-month follow-up interview, all participants will complete the Client Satisfaction Questionnaire (CSQ)¹⁴ to assess satisfaction with and acceptability of the intervention. The CSQ is an 8-item, easily scored and administered measurement that is designed to measure client satisfaction with services. The items for the CSQ-8 were selected on the basis of ratings by mental health professionals of a number of items that could be related to client satisfaction and by subsequent factor analysis. The CSQ has demonstrated adequate reliability and validity (Cronbach's alpha 0.90) in various samples^{15,16}. Two additional open questions will be included to assess the participants' perception of therapist competence and offer the opportunity to make any other comments regarding the treatment. The practicalities of recruitment will be assessed descriptively. Refusal and dropout from the study protocol will be recorded. Rates of withdrawal from treatment will be calculated as a percentage of those randomized. A schedule of study visits is displayed in Table 2.

Table 2. Scheduled visits

	Enrollment	BBTI + eszopiclone		BBTI	
		EOT	6-month	EOT	6-month
Procedure & Assessment					
Informed Consent	•				
Demographics	•				
ESS	•	•	•	•	•
PCL-5	•	•	•	•	•
PSQI	•	•	•	•	•
ASI-Lite	•	•	•	•	•
Insomnia Severity Index (ISI)	•	•	•	•	•
Beck's Depression Inventory	•	•	•	•	•
CSQ			•		•
CPAP adherence		•	•	•	•
Medication Review	•	•	•	•	•
Actigraphy	•	•	•	•	•

6.7 *Training and Monitoring of treatment delivery*

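### Structured adverse-event monitoring during the 2-week medication period is described only for the combination arm, so early adverse events cannot be compared like for like

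*Combined protocol and SAP*

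**What the plan says.** Section 6.5, part B describes what the combination arm receives in addition to the behavioral treatment: "participants randomized to the combination therapy will receive eszopiclone 2 mg orally at bedtime or placebo starting with the CBT-I sessions", for 2 weeks. The safety monitoring is set out in the same paragraph. A "consultation session during the enrollment visit will be provided to review potential side effects that could arise from the medication". Then: "The Patient Monitoring Checklist will be obtained at baseline (enrollment), week 1, and at week 2". And: "The study pharmacist will review the Patient Monitoring Checklist to assess for serious adverse events".

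Section 6.5, part A describes the behavioral treatment: in-person visits at weeks 1 and 3, and "brief telephone appointments during weeks 2 and 4". The stated content of these contacts is the sleep schedule, adherence and support. No adverse-event question is mentioned. The one prompt given to all participants at every call and visit concerns CPAP problems.

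Section 6.6 applies to both arms: "Follow up visits for all participants will be scheduled at EOT and at 6-month". At those visits, "Potential adverse events will be assessed including hospitalization, and extreme sleepiness". Table 2 has no row for the checklist or for adverse events. The Statistical and Analytical Plans section specifies no between-arm safety analysis and does not say which adverse-event source a summary would use.

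**The concern.** The trial compares adding a drug to BBTI with not adding it, so readers will want to know what the drug adds in harm as well as in benefit. As written, the combination arm is asked about problems on a structured form twice after baseline, around the period of drug exposure. The BBTI-alone arm is not asked until EOT. More frequent prompting usually yields more recorded events, whatever the true risk.

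The BBTI-alone arm also has something to monitor. Its participants have sleep apnea, are not adherent to CPAP and have their time in bed restricted; the protocol itself sets a 6-hour floor on safety grounds. Extreme sleepiness, including while driving, is one of the events section 6.6 asks about. Without an earlier prompt, such events in the first weeks would be recorded later or less completely in that arm.

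**Working it through.** The plan states no event rate or safety power, so there is no figure to reproduce. The check is a comparison of the arms by time point, followed by an illustration.

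**Stated adverse-event assessment, by arm**

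| Time | Combination arm | BBTI alone |
|---|---|---|
| Enrollment | Checklist; side-effect consultation | None stated |
| Week 1 | Checklist | None stated (BBTI visit takes place) |
| Week 2 | Checklist | None stated (BBTI call takes place) |
| Weeks 3 and 4 | None stated | None stated |
| EOT | Assessed | Assessed |
| 6 months | Assessed | Assessed |

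Three further points come from reading the sections together.

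1. *Recall.* Medication lasts 2 weeks, BBTI lasts four, and EOT is not tied to a week. If EOT follows the fourth BBTI week, it looks back on a drug period that ended about two weeks before.
2. *Who is covered.* Section 6.4 says "Participants who complete all baseline assessments will be randomized". A form completed at enrollment therefore precedes allocation and cannot be restricted to one arm. Part B also mentions placebo, while section 6.4 gives BBTI alone as the comparator. It is not fully clear to whom part B applies.
3. *What week 1 means.* The week-1 visit is the first BBTI session, and medication starts with the sessions. A checklist completed at that visit would come before any exposure to drug or sleep restriction. One completed a week later would not.

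**Illustration (all values assumed)**

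Recorded risk = true risk × probability of capture. Take a true risk of 20% in both arms and capture of 90% with the checklist.

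| Capture without checklist | Recorded, combination | Recorded, BBTI alone | Difference | Ratio |
|---|---|---|---|---|
| 90% | 0.20 × 0.90 = 0.18 | 0.20 × 0.90 = 0.18 | 0 | 1.0 |
| 70% | 0.18 | 0.20 × 0.70 = 0.14 | 0.04 | 1.29 |
| 50% | 0.18 | 0.20 × 0.50 = 0.10 | 0.08 | 1.8 |

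The true risk cancels from the ratio, which is simply 0.90 divided by the other capture probability. At a true risk of 40% the ratios are unchanged and the differences double to 0.08 and 0.16.

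Section 8.0 plans 52 participants and section 6.4 allocates 1:1, so if all 52 are randomized there are 52 / 2 = 26 per arm. At 20% risk the expected recorded counts are 26 × 0.18 = 4.7, against 26 × 0.14 = 3.6 or 26 × 0.10 = 2.6: a gap of about one or two participants.

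**The case against.** A reader might infer that the safety of the two arms cannot be compared fairly at all, that the drug's harm will be overstated, or that early sleepiness on BBTI alone will be missed. The documents support none of these.

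- Section 6.6 gives both arms the same adverse-event assessment at EOT and 6 months, and the Epworth Sleepiness Scale is collected in both arms at those visits. A comparison restricted to these visits is free of the difference in schedule.
- No analysis pooling checklist events with visit events is planned. The bias arises only if someone pools them.
- Extreme sleepiness is asked about in both arms at EOT, so later or less complete capture is the most that can be claimed.

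It is also fair to say that closer monitoring of people taking a drug is ordinary protection and not an error. The pharmacist reviews the form for serious events, and a hospitalization is less likely to be forgotten by EOT than a minor complaint, so 50% capture may be too pessimistic for serious events. The content of the checklist is not in the documents; if its items are specific to the drug, some would mean little on BBTI alone.

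These points narrow the concern but do not remove it. The common visits do not give equal information on the 2-week drug period. The plan promises descriptive statistics for all variables, so an adverse-event table by arm is likely, and nothing says which source it would draw on. The combination arm would also arrive at EOT after a side-effect consultation and two post-baseline checklists, which could prime reporting; that is an inference and not something the documents state.

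**Conclusion.** The point holds in a limited form. As written, adverse-event ascertainment is unequal between the arms during the medication period, and early events cannot be compared like for like. If checklist events enter a by-arm summary, the combination arm could look worse for that reason alone. The scheduled EOT and 6-month assessments remain comparable.

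The size is not known. A ratio of 1.0 (equal capture) to about 1.3 or 1.8 (70% or 50% capture against 90%) rests wholly on assumed capture rates. The effect is likely to be larger for non-serious events than for hospitalization. The conclusion also assumes that part B applies only to the combination arm, which its placement and opening sentence suggest but its mention of placebo leaves open. The primary analysis of PSQI is not affected. The change is worth making because it is cheap, removes an avoidable asymmetry and adds early safety capture for the BBTI-alone arm.

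**What to change.** 1. Obtain the same checklist, with the same pharmacist review, in both arms at enrollment and at matching existing contacts after treatment has started. The week-2 call and the week-3 visit would serve, since they look back on the first and second treatment weeks. Using the week-1 visit would not, because treatment only begins there.
2. Define what week 1 and week 2 mean for the checklist, and tie EOT to a study week.
3. State that by-arm adverse-event tables use only sources collected identically in both arms. Report separately any checklist events collected only in the combination arm. If the checklist is not extended, the tables would rest on the EOT and 6-month assessments.
4. Add checklist and adverse-event rows to Table 2.
5. Reconcile the mention of placebo in section 6.5, part B with the BBTI-alone comparator in section 6.4, so that it is clear who is covered.

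The cost is a few minutes at existing contacts for about 26 more participants and pharmacist review of those forms. No new visits are needed. Items 2 to 5 are edits to the text.

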A pragmatic randomized comparator trial of
eszopiclone and brief behavioral therapy for
insomnia in CPAP non adherent Veterans with
PTSD and complex insomnia

NCT03937713

June 5, 2020

RESEARCH DESIGN AND METHODS

The current application proposes to explore the comparative effectiveness of combination therapy of behavioral and pharmacological interventions with behavioral therapy alone in improving the sleep quality of life of Veterans with COMISA.

Trial design

This trial will follow the International CONSORT (Consolidated Standards of Reporting Trials) guidelines using a randomized trial design ¹. The trial will be registered at clinicaltrials.gov.

Study population

Participants will be recruited from the sleep clinics at the VA Western New York Healthcare System. The clinics operate 8 sessions per week with more than 3,500 visits per year. A written waiver of consent and partial waiver of HIPAA authorization will be requested to collect and review health information about prospective subjects prior to obtaining written informed consent. The waiver will not adversely affect the rights and welfare of the subjects, and the research could not be conducted without the waiver because the health information collected is necessary to ascertain which subjects are eligible to participate in the study.

Inclusion criteria: Subjects who fulfill the following criteria at screening will be included in the study:

- Age >18 years and <65 years old (the reason for limiting recruitment for combat-exposed Veterans between 18 and 65 years of age is due to the change in pharmacodynamics of eszopiclone in patients above 65 years old. Compared to nonelderly adults, a 41% increase in the AUC and a prolonged elimination ($t_{1/2}$ life) of approximately 9 hours were observed in subjects 65 years and older)²
- Documented obstructive sleep apnea by polysomnography (AHI \geq 5 or more/hour) who are non-adherent to CPAP as defined by device usage of less than 4 hours per night
- Chronic (\geq 3 months' duration) insomnia disorder (based on International Classification of Sleep Disorders, Second Edition (ICSD-2) criteria). The Diagnostic and Statistical Manual, 5th edition (DSM-5) defines insomnia as difficulty falling or staying asleep, or non-restorative sleep, at least 3 nights per week, with sleep-related distress or daytime dysfunction, for at least 3 months
- Psychotherapeutic treatment stable for at least 4 weeks prior to randomization

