Treatment fidelity: To ensure treatment fidelity, the PI will randomly select 20% of the audiotapes and forward to [name] for adherence and competence ratings, using a modified version of the Competence and Adherence Scale for cognitive behavioral therapy ¹⁷. In case it is determined that the research coordinator has deviated significantly from the protocol, he/she will be assigned to 3 practice/training cases/week under close supervision with intensified tape rating until the original certification level has been reestablished. In addition, ongoing supervision and the provision of corrective feedback are critical to avoid therapist "drift" and ensure continued fidelity of treatment. The therapeutic value of CBT in randomized controlled trials appears particularly dependent on the quality of supervision. Controlled trials that have incorporated more intensive supervision have yielded stronger outcome data ¹⁸. Proper supervision would include two components: 1) continuous monitoring of treatment delivery and 2) provision of corrective action. We will adopt the supervisory model of a well administered multicenter trial (the Enhancing Recovery in Coronary Heart Disease) that featured CBT for depression and low social support for post MI-patients ¹⁸. The model would include biweekly meetings of the research coordinator with the PI, review of audiotapes, and self-monitoring of the administered therapy through checklists.

Outcome measures

The Pittsburgh Sleep Quality Index (PSQI)¹⁹ The PSQI is a 19-item, self-rated questionnaire, assessed various aspects of sleep, sleep quality, and sleep disturbances over the previous month. Psychometric evaluation of the scale supports its internal consistency reliability and construct validity, and the scale is highly sensitive and specific for the identification of sleep disturbances in a variety of clinical populations²⁰. The PSQI is composed of 7 components: subjective sleep quality, sleep latency, sleep duration, habitual sleep efficiency, sleep disturbances, use of sleeping medication, and daytime dysfunction. The sum of scores for these 7 components yields 1 global score. Total PSQI scores > 5 have yielded a diagnostic sensitivity of 89.6% and a specificity of 86.5% in distinguishing poor sleepers from good sleepers.

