Other (secondary) measures of CPAP adherence will include also average hours of use per night and usage index which will be calculated as the number of days the CPAP was used for more than 4 hours divided by the total number of days studied.

Statistical and Analytical Plans

Data analysis will consist of descriptive statistics of all variables and constructs. These will include counts and percentages for binary and categorical variables and means and standard deviations, or medians with lower and upper quartiles, for continuous variables, along with minimum and maximum values and counts of missing values. Data distributions and all model assumptions will be checked for all analyses. If model assumptions are not met, data will either be transformed or analyzed using a non-parametric test, as appropriate. The descriptive statistics will ensure that our randomization process is effective and that no statistical differences exist between the study population. In the event that key differences emerge, weighting procedures will be used in the analysis to control for these baseline differences. The intent-to-treat (ITT) protocol will be followed for these analysis²². We plan also on following up all participants enrolled in the study independent of whether they complete treatment so that we can perform both per protocol (PP) as well as intent-to-treat analyses. Per protocol analyses focus evaluation only on those individuals who complete treatment. The logic is that to evaluate the effectiveness of a treatment protocol, analyses should be conducted on those who received “full dose” of the treatment. By contrast, ITT analyses place greater emphasis on external validity and focuses on the real world impact of the treatment taking into account that individuals may choose to drop out of treatment because of the nature of the treatment itself. In ITT analyses, all respondents who are initially randomly assigned to the various experimental conditions are analyzed to the posttests²³ whereas in PP analyses, only those who complete the treatment protocol are analyzed. Both forms of analyses are informative, and we will approach the data from each perspective.

Analysis plan for the primary outcome

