Our primary strategy is to compare BBTI plus eszopiclone versus BBTI using analyses that are straightforward and highly interpretable while still accounting for other important covariates. Within-subject changes in the PSQI from baseline will be **the primary outcome**. The primary analyses involve the statistical assessment of group differences with regards to this outcome and will be based on a linear model. In taking this approach, we fit the dependent variable as a linear function of independent variables treatment regimen, and baseline outcome level. Rather than utilizing the null distribution associated with the classic F-test for treatment differences within this framework which is dependent on the validity of distributional assumptions, an exact permutation testing approach will be utilized. The randomization mechanism at work is a crucial component in this study in that it will be used to create the randomization distribution by which statistical significance will be determined. For more on this approach see Gail, Tan, and Piantadosi (1988)²⁴. Reported p-values will be obtained from the permutation distributions of the test statistics based on 10,000 Monte Carlo simulations. As secondary analyses, additional subject covariates will be included as independent variables. The interaction of the treatment group and subject covariates may also be examined in a secondary fashion in order to identify possible differential effects of treatment. All statistical tests will be two-sided and tested at a 0.05 nominal significance level.

Analysis plan for the secondary outcomes

Analyses of secondary outcomes will proceed in a similar fashion. For actigraphy outcomes, data will be averaged over one-week periods. Alpha level will be adjusted using the Bonferroni correction when indicated. All analyses will be carried out using SAS version 9.4 (or higher) statistical software (Cary, NC).

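### The primary PSQI score counts sleeping-medication use, only one arm is assigned a hypnotic, and no analysis without that component is prespecified

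*Combined protocol and SAP*

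**What the plan says.** *Analysis plan for the primary outcome* defines the endpoint in these terms: "Within-subject changes in the PSQI from baseline will be" the primary outcome. It names neither a visit nor a subset of components. Under *Outcome measures*, the PSQI is described as an instrument that "assessed various aspects of sleep, sleep quality, and sleep disturbances over the previous month". Its component list ends with "use of sleeping medication, and daytime dysfunction. The sum of scores for these 7 components yields 1 global score". A score above 5 marks a poor sleeper, so higher is worse.

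The opening section sets the aim as the "comparative effectiveness of combination therapy of behavioral and pharmacological interventions with behavioral therapy alone". Section 6.4 and Table 2 name two arms, BBTI plus eszopiclone and BBTI. Section 6.5 B states that the combination arm "will receive eszopiclone 2 mg orally at bedtime or placebo starting with the CBT-I sessions for a period of 2 weeks". Section 6.5 A runs BBTI over four weeks, and section 6.6 places follow-up at EOT and 6 months without dating EOT. The exclusion criteria bar people already on drug treatment for insomnia.

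For the analysis, "we fit the dependent variable as a linear function of independent variables treatment regimen, and baseline outcome level", with a permutation test. Beyond that, "As secondary analyses, additional subject covariates will be included as independent variables", and interactions may be examined. *Statistical and Analytical Plans* adds a second analysis set: "Per protocol analyses focus evaluation only on those individuals who complete treatment". Nothing drops or separates the medication component, or says how trial-supplied eszopiclone is to be scored on it.

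**The concern.** The outcome contains a component that assignment itself can move, in one arm and in the unfavourable direction. Because current insomnia drug treatment is an exclusion, the component probably starts low in both arms, although no washout is stated. A rise in the combination arm at EOT could then simply record the study drug.

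A small PSQI difference at EOT would have two readings: little added sleep benefit, or real benefit partly cancelled by the medication component. The plan has no prespecified way to tell them apart. Dropping the component only after an unfavourable result would look selective. The per-protocol analysis does not help, because treatment completers are the group in whom this shift would be least diluted.

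**Working it through.** **Inputs from the plan.** Section 8.0: SD 3.5, difference 3 units, 21 per group, about 80% power, baseline to follow-up correlation 0.7. *Analysis plan for the primary outcome*: two-sided 0.05. Sections 6.5 A and B: four weeks of BBTI, with two weeks of drug starting with the sessions. *Outcome measures*: one-month recall.

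**Assumptions, not in the documents.** Net between-arm shift in the medication component *s* = 0.5, 1 or 2 points; component range 0 to 3; a month taken as 28 nights; drug taken on nights 1 to 14.

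**1. The plan's own figure.** The standard error is 3.5 × √(2/21) = 1.080, and 3/1.080 = 2.78. The normal approximation gives power Φ(2.78 − 1.96) = 0.793, and 22 per group for 80%. The exact noncentral-t power on 40 df is 0.773. The stated 21 per group and roughly 80% therefore match the unadjusted SD of 3.5 closely.

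**2. The offset.** The global score is a plain sum, so

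full-score difference = six-component benefit − *s*.

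A 3-unit full-score difference then needs a six-component benefit of 3 + *s*. Planned power for a 3-unit difference on the full score is unchanged.

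**3. Illustration.** If the true benefit on the other six components is 3 units, the full-score difference is 3 − *s*. Exact-t power at 21 per group:

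| *s* | *s*/3 | six-component benefit needed for 3 on the full score | full-score difference if six-component benefit is 3 | power, SD 3.5 | power, SD 2.50 |
|---|---|---|---|---|---|
| 0 | 0% | 3 | 3 | 0.773 | 0.967 |
| 0.5 | 17% | 3.5 | 2.5 | 0.617 | 0.885 |
| 1 | 33% | 4 | 2 | 0.439 | 0.716 |
| 2 | 67% | 5 | 1 | 0.148 | 0.244 |

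The last column uses the baseline-adjusted SD, 3.5 × √(1 − 0.7²) = 2.50. It treats 3.5 as the SD at a single visit, which the plan does not say.

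**4. Which visits are exposed.** A 28-night window ending at week *k* covers nights 7*k* − 27 to 7*k*. Drug nights inside it are:

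- *k* = 2, 3 or 4: all 14
- *k* = 5: 7
- *k* = 6 or later: 0

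The two natural readings of EOT, end of drug (week 2) and end of BBTI (week 4), both give full overlap. The study drug cannot act through this component at 6 months. The documents give no conversion from nights to points.

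**5. Whether the planned model removes it.** The shift arises after randomization, so adjusting for baseline PSQI leaves it in the treatment coefficient. The permutation test asks whether assignment changes the score at all, and does not separate a medication-component effect from a sleep effect. Adding covariates does not change what the outcome contains.

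**The case against.** The strongest reply is that the problem is conditional and unsized. It reaches the primary result only if EOT is the primary visit and falls by about week 5, and the plan states neither. The missing primary visit is arguably the more basic gap. Section 6.5 B mentions placebo, and placebo in the BBTI arm would largely remove the artefact. The component's scoring is not given, and a 2-point shift from 14 nights of drug is supported by nothing in the documents. With the adjusted SD of 2.50, a half-point shift still leaves power of 0.885. ISI and actigraphy list no medication component, and the promised descriptive statistics could include the PSQI components. In the per-protocol set, completers would keep more of any drug benefit as well as more of the shift, so a weaker per-protocol result is not predicted.

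The points on timing, size and net direction stand as limits. So does the per-protocol point, especially as the plan does not say whether completion means drug, BBTI or both. The rest does not remove the concern. The placebo wording appears only in the combination-arm description; as written, the BBTI arm is assigned no pill. The smaller SD softens the power illustration but not the one-for-one offset in the estimate. ISI and actigraphy could flag a discordant PSQI result, but they cannot show how much of it comes from this component. A general promise of descriptive statistics does not commit to a six-component model or a component table by arm and visit.

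**Conclusion.** The concern holds and should be fixed, with medium confidence. As written, the primary score can register the assigned hypnotic as worse sleep at EOT in one arm only, and no prespecified analysis isolates this. The component effect would mask benefit of the combination, not create it. Its size is unknown: net shifts of 0.5, 1 or 2 points, all assumed, would offset 17%, 33% or 67% of the 3-unit difference.

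The conclusion rests on EOT falling within about five weeks of starting the drug, on no pill being assigned to the BBTI arm, and on participants counting study drug when they answer. The net bias is not established: non-study hypnotics may arise in either arm, and unblinded self-report could push the other way. None of this shows that the planned power is wrong.

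**What to change.** Keep the seven-component global score as primary. Prespecify, as a key sensitivity analysis, a six-component PSQI sum that omits sleeping-medication use. Score it identically at baseline and follow-up in both arms, and analyse it with the same linear model and permutation test. Report it beside the primary result in both the ITT and per-protocol sets, with the medication component tabulated by arm and visit. State that the 3-unit difference and the SD of 3.5 refer to the full score.

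Separately, state the primary visit and the week of EOT, and reconcile the placebo wording in section 6.5 B with the opening section, section 6.4 and Table 2.

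The cost is one scoring rule, one extra model run per analysis set and one descriptive table. The PSQI is already collected at enrollment, EOT and 6 months. The downside is that the plan documents no SD, important difference or cutoff for a six-component sum, so it should be read by its estimate and interval. With 21 per group the 95% half-width is t(0.975, 40) × SD × √(2/21), which is 1.87, 2.18 or 2.49 points for an assumed SD of 3.0, 3.5 or 4.0.
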